12.3 Safety Assessments

The description of safety assessments is given below, and the timings of these assessments is given in the Schedule of Assessments. The time points of the safety assessments may change depending on information gained throughout the study, however the total number of safety assessments per volunteer will not be reduced, although unscheduled assessments may be performed at the discretion of the Investigator.

12.3.1 Clinical Laboratory Tests

The following parameters will be measured:

Haematology

Red blood cell count

Haemoglobin

Haematocrit

Platelet count

White blood cell count with absolute differential (neutrophils, lymphocytes, monocytes, eosinophils, basophils)

Biochemistry

Sodium

Potassium

Chloride

Bicarbonate

Blood urea

Creatinine
Creatine Kinase
Glucose (in a fasting state at screening)
Calcium
Albumin
Cholesterol
Triglycerides
Phosphorus (inorganic phosphate)
Lactate dehydrogenase (LDH)
Total protein
Globulin
Uric acid
Alkaline phosphatase (ALP)
Aspartate aminotransferase (AST)
Alanine aminotransferase (ALT)
Gamma-glutamyl-transferase (GGT)
Total bilirubin
Direct bilirubin

Urinalysis

Specific gravity
pH
Protein
Glucose
Ketone
Occult blood
Leukocyte esterase
Nitrites

Additional urine microscopy analysis will be undertaken, if any abnormalities are detected, to analyse for red blood cells, white blood cells, epithelial cells, bacteria, casts, and crystals.

12.3.2 ECGs and Vital Signs

ECGs will be recorded after the volunteer has been lying for at least 5 minutes.

Vital signs will be recorded in the supine position, after the volunteer has been lying for at least 5 minutes. The normal ranges for vital signs are:

Systolic blood pressure	90-140 mmHg
Diastolic blood pressure	40-90 mmHg
Pulse rate	40-100 bpm
Respiration rate	10-20 breaths per minute
Temperature	$\geq 35.8^{\circ}\text{C}$ and $\leq 38^{\circ}\text{C}$

12.3.3 Injection Site Tolerability Assessment

Injection site tolerability assessments will be performed as described in Appendix 1.

12.4 Time Windows for Visits

Vital signs will be performed within ± 10 minutes of the scheduled time.

The time window for Visits 3 and 7 is ± 2 hours.

The time window for Visits 4, 5, 6, 8, 9 and 10 is ± 1 day.

The time window for Visit 11 in Part A is ± 1 week.

The time window for visits from Visit 11 in Part B onwards is ± 3 weeks.

12.5 Safety Monitoring Board and Safety Data Review Meetings (Part A only)

All cohorts in Part A will incorporate sentinel dosing of 2 volunteers in each cohort for the primary dose only: 1 on active treatment and 1 on placebo. No further volunteers in that cohort will be dosed until at least 24 hours after dosing the second volunteer, provided that there are no serious or unexplained safety issues as determined by the Investigator.

In Part A, the decision to proceed with administration of the primary dose in subsequent cohorts will be made as follows:

- Safety will be assessed after at least 7 evaluable volunteers in cohort 1 (sentinel and main) have completed Visit 4 (Day 8), at which point the decision will be made to proceed with administration of the primary dose in cohorts 2 and 3.
- Safety will be assessed after at least 7 evaluable volunteers in each of cohorts 2 and 3 have completed Visit 4 (Day 8), at which point the decision will be made to proceed with administration of the primary dose in both cohorts 4 and 5 or just one of these cohorts.
- Safety will be assessed after at least 7 evaluable volunteers in each of cohorts 4 and 5 have completed Visit 4 (Day 8), at which point the decision will be made to proceed with administration of the primary dose in cohort 6.

The following safety data will be reviewed:

- Clinical Laboratory Tests
- ECGs
- Vital signs
- Physical examinations
- Assessment of injection site reactions
- AEs

The Safety Monitoring Board will include two voting members - the Principal Investigator and Sponsor's Medical Monitor. If a voting member is unable to attend a Safety Data Review Meeting, a designated back-up can attend on their behalf and act as a voting member. Designated back-ups must be agreed and documented in advance. Non-voting members may also be part of the Safety Monitoring Board.

The Safety Monitoring Board will meet in person or by teleconference at scheduled Safety Data Review Meetings at which the safety data will be reviewed. A summary of safety data will be provided for review, including safety data entered on to the electronic CRF

(eCRF) by the site and clinical laboratory test results transferred to the Data Management provider from the safety laboratory.

After review and discussion of all the data, the decision will be made on dose escalation and documented by signature of the Dose Escalation Approval Form by the voting members of the Safety Monitoring Board. Minutes documenting the main points discussed and decisions made regarding dose escalation will be produced. The minutes will be agreed by all parties and filed in the site Trial Master File.

At least 7 evaluable volunteers in Part A are required to complete through visit 4 in each cohort in order to provide sufficient data for a decision to dose escalate. If the required number of evaluable volunteers are not obtained in a cohort, then replacement volunteers must be dosed for that cohort, prior to considering dose escalation. The Safety Monitoring Board may also decide to repeat a dose level or choose an intermediate dose.

Progression to the next higher dose level will be stopped if any of the study stopping criteria are met as described in Section 12.7. Individual volunteers will be discontinued from the study if they meet any of the individual volunteer stopping criteria as described in Section 12.6.

In Part B, sentinel dosing is not required, and volunteers in all groups may be randomised and dosed concurrently.

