12.7 Study Stopping Criteria

A Safety Review Meeting will be convened to determine the progression of the study if any of the following scenarios occur:

- If one of the sentinel group or more than 20% of the volunteers in a cohort experience a severe site reaction.
- If one of the sentinel group or more than 20% of the volunteers in a cohort experience a severe systemic reaction.
- If one of the sentinel group or more than 20% of the volunteers in a cohort experience a persistent febrile reaction (>38.9°C and >24 hours)
- 1 or more volunteers experience a SAE related to the study agent.

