14.5 Reporting Timelines

14.5.1 SAE Reporting

An SAE must be reported immediately (within 24 hours), independent of the circumstances or suspected cause, if it occurs or comes to the attention of the Investigator at any time during the study period. Any SAE with a suspected causal relationship to the IMP occurring at any other time after completion of the study must be promptly reported.

Contact Details for SAE Reporting:

The following mandatory information must be provided to the Sponsor pharmacovigilance contact within 24 hours for each SAE:

- Protocol number
- Volunteer number
- AE
- IMP
- Investigator's name and contact details

Causality assessment should be completed as soon as possible.

Follow-up information should be actively sought until the SAE has resolved or sequelae have stabilised. Additional information e.g. hospital reports or death certificates, may be requested by the Sponsor and should be anonymised/pseudonymised before transmission and subsequently filed in the Investigator Site File.

The expectedness of an SAE shall be determined by the Sponsor according to the most recent version of the Investigator's Brochure.

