15.2 Studied populations for each study part

The following populations will be taken into account for each study part:

- **Intention to Treat Set (ITT):** All included volunteers who receive at least one dose of the study vaccine will be taken into account in the description of the population (disposition, demographic or baseline characteristics);
- **Immunogenicity Set (IG):** The subset of volunteers who will receive at least one dose of the study vaccine with available pre- and post-vaccination titers.
- **Per Protocol Set (PP):** All volunteers who receive both doses of the study vaccine and provide evaluable samples for analysis of the primary immunological endpoint and do not violate the protocol.

The Primary and Secondary Safety analyses will be performed on the ITT set. The Secondary Immunological analyses will be performed on the IG set. The “primary” immunological analysis (i.e. the results on Day 85 in both study parts) will also be performed on the PP set.

Missing or incomplete data will not be replaced, unless otherwise specified (example: values strictly under the LLOQ for immunogenicity data).

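### In Part A a met stopping criterion halts escalation, but nothing written pauses the remaining primary or booster doses in the same cohort until the safety meeting

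*Combined protocol and SAP*

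**What the plan says.** Two sections set out what follows when a study stopping criterion is met in Part A.

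- Section 12.5: "Progression to the next higher dose level will be stopped if any of the study stopping criteria are met".
- Section 12.7: "A Safety Review Meeting will be convened to determine the progression of the study if any of the following scenarios occur". The scenarios are a severe site reaction, a severe systemic reaction or a persistent fever, each in one sentinel or in more than 20% of a cohort, and one or more related SAEs.

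Other controls bear on dosing within a cohort.

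- Sentinels (12.5): "All cohorts in Part A will incorporate sentinel dosing of 2 volunteers in each cohort for the primary dose only". The hold reads: "No further volunteers in that cohort will be dosed until at least 24 hours after dosing the second volunteer". It is released if the Investigator sees no serious or unexplained problem.
- Section 12.6 ends dosing for the volunteer who meets an individual criterion.
- Section 9.5 allows the whole study to be stopped for unforeseen safety concerns. Section 9.7 allows early termination after review by sponsor and Investigator.
- Section 12.2.1 makes the Visit 6 booster depend on a committee decision for each cohort. Section 6.2 places that decision at the escalation review.
- Section 12.4: "The time window for Visits 4, 5, 6, 8, 9 and 10 is ± 1 day".

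Section 12.5 schedules three reviews: after cohort 1, after cohorts 2 and 3, and after cohorts 4 and 5. The last one opens cohort 6.

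**The concern.** Written stopping criteria fix the response before the event. Here the triggers are defined, but the immediate action on doses still due at the current level is not. The one automatic stop concerns the next level up. The people most directly at risk after a trigger are the rest of the same cohort, who are due the same product at the same dose.

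Two situations stand out. Boosters have no sentinel step, although section 12.2.1 itself names an acute systemic reaction after the booster as the concern. Cohort 6 receives the highest planned dose with adjuvant, so there is no higher level for the automatic stop to act on. Optional cohort 7, if opened, may not exceed 250 µg. The vaccine had not been given to humans before this trial (section 6.3).

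**Working it through.** The plan gives no figure for this rule, so there is none to reproduce. The check is to compare the text with each kind of dose and then count who could be due one.

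**Step 1. Which control pauses which dose between trigger and meeting?**

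| Dose still due | Written automatic pause? |
|---|---|
| Next higher level | Yes (12.5) |
| Next dose of the affected volunteer | Yes (12.6) |
| Main-group primary doses, same cohort | Only during the sentinel hold |
| Boosters of the others, same cohort | None; no re-check is stated once boosting has begun |
| Cohort 6, any remaining dose of the others | As the two rows above; the escalation stop has nothing to act on |

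**Step 2. Inputs.** A cohort has 10 volunteers, 8 active and 2 placebo (12.2.1). The sentinels are 1 active and 1 placebo (12.5). The main group is therefore 10 − 2 = 8, of whom 8 − 1 = 7 are active. More than 20% of 10 means at least 3, because 2 of 10 is exactly 20%.

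**Step 3. Doses outstanding per trigger.**

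| Trigger (affected volunteers on active vaccine) | Volunteers left | Active left |
|---|---|---|
| Related SAE in the first volunteer boosted | 10 − 1 = 9 | 8 − 1 = 7 |
| Same, active sentinel affected, both sentinels already boosted | 10 − 2 = 8 | 8 − 1 = 7 |
| Sentinel criterion met after the primary-dose hold is released, main group not yet dosed | 10 − 2 = 8 | 8 − 1 = 7 |
| Related SAE in the first main-group volunteer given the primary dose | 8 − 1 = 7 | 7 − 1 = 6 |
| Three of 10 with a severe reaction, boosters still to come | 10 − 3 = 7 | 8 − 3 = 5 |
| Meeting held before the next dose, or event after the last booster | 0 | 0 |

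The trial is blinded, so an event in a placebo recipient could also be judged related. Then 9 remain, 8 of them active.

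**Step 4. How quickly the doses fall due (assumed schedule).** Suppose both sentinels are dosed on Day 1 and the whole main group on Day 2, the earliest that the hold allows. Boosters are then due on Days 29 and 30. With ±1 day, sentinels fall on Days 28 to 30 and the main group on Days 29 to 31. The last booster comes at most 31 − 28 = 3 days after the first. At nominal dates, a meeting before the next dose exposes nobody, and a lag of one day or more leaves 8 to 9 volunteers due.

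**Step 5. How often a trigger might occur.** The documents give no event rates, so these are illustrations: 8 active volunteers, independent events, none on placebo.

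- At least one related SAE, 1 − (1 − p)^8: 0.149 at p = 2%, 0.337 at p = 5%.
- At least 3 of 8 with one type of severe reaction (binomial tail): 0.038, 0.203 and 0.448 at 10%, 20% and 30%.

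The finding does not depend on these rates.

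**The case against.** The strongest reply is that section 12.7 is titled as stopping criteria for the study and its meeting decides how the study goes on, so a pause is implied. Section 9.5 makes the sponsor or Investigator responsible for withdrawing a volunteer when that is in her interest, and section 12.6 closes by putting medical safety first. Boosted volunteers stay at least 4 hours, are examined before discharge and return at 24 hours, so an acute reaction would usually be seen on site before the next group is due. A meeting can be by teleconference. All of this stands, and it is why the lower end of the range is 0. It does not supply a rule: a reasonable site would probably hold, but the plan leaves that to inference.

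A reader might infer more than the documents support:

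- **That the plan has dosing continue after a trigger.** It is silent; it neither requires nor forbids a hold.
- **That cohort 6 boosters have no gate.** Section 12.2.1 requires a committee decision for each cohort. What is missing is a pause once that decision has been made.
- **That the 24-hour SAE reporting limit hides events from the decision-makers.** The limit governs notice to the sponsor. The trial has one centre, and its Principal Investigator is a voting member.
- **That the fever criterion defeats the sentinel hold because it needs more than 24 hours.** The hold is a minimum, and its release condition is broader than 12.7.
- **That the per-protocol definition penalises a hold.** Section 15.2 asks that these volunteers "provide evaluable samples for analysis of the primary immunological endpoint and do not violate the protocol", but nothing says that a safety delay is a violation, and safety is analysed on the ITT set.
- **That every booster given after cohort 6 opens is exposed.** Only doses due between a trigger and its meeting are.

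A hold can also be set off by a minor event: Appendix 1 grades bruising above 5 cm as severe, and one such bruise in a placebo sentinel would count. That is a reason to confine the automatic hold to the affected cohort.

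**Conclusion.** The point holds as a gap in a safety rule. When a 12.7 criterion is met in Part A, escalation stops and a meeting is called, but no text suspends the doses still due in the same cohort and no deadline is set for the meeting. The size is 0 to 9 volunteers per trigger, up to 7 of them active if the affected volunteer was active. The upper end needs an event in the first volunteer boosted and a meeting that comes after the others' due dates. Neither the dosing days nor the meeting lag is given, so the position within the range is unknown. This should be corrected because the trial is first-in-human and the remedy is small. It does not show that any volunteer would in fact be dosed after a trigger.

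**What to change.** Add to section 12.7: when any criterion is met in Part A, all further primary and booster dosing in the affected cohort is suspended at once. Dosing resumes only on a documented decision of the Safety Review Meeting, signed by the voting members of the Safety Monitoring Board, who also decide whether other open cohorts are held. With such a hold in place, the missing deadline matters much less, because nobody in the affected cohort is dosed while waiting.

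Add to section 12.4: a booster delayed by such a hold may be given outside the ±1 day window.

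The cost is a few sentences, with no extra volunteers, visits or samples. Some boosters may be delayed by a few days. Visits 9 and 10 are timed from the first dose, so a delay of d days shortens the booster-to-sample interval from 57 − 29 = 28 to 28 − d days at Day 57, and from 85 − 29 = 56 to 56 − d days at Day 85. Day 57 informs the Part B dose choice, so report the actual interval for those volunteers.

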9.5 Volunteer Withdrawal

The volunteer has the right to abstain from participation in the study or to withdraw consent to participate at any time without penalty. The Sponsor or the Investigator also holds the responsibility to withdraw a randomised volunteer from the study prematurely if it is considered in the best interest of the volunteer. The entire study may be stopped if there are unpredicted safety concerns.

A volunteer's participation may be discontinued at any point during the study without implications on further medical care if:

- They no longer wish to participate.
- The physician feels it is in their best interest to withdraw.
- The volunteer deviates from the treatment plan specified in the protocol (e.g. failure to attend study visits).
- The volunteer is no longer willing to comply with the requirements of the study protocol.
- The study is prematurely terminated, see Section 9.7.

If the participation of any volunteer ceases prematurely, the reasons leading to withdrawal from the study should be described in detail. A post-study medical should be performed as described in Section 12.2. The case report form (CRF) must be completed as fully as possible giving reasons for withdrawal when available.

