Visit 9 will be performed 8 weeks following the first study vaccine administration and the following assessments will be performed: an assessment of the injection site and a pharmacodynamic blood sample will be taken to measure antibody response and AEs and concomitant medications will be reviewed.

Post-Study Medical (Visit 10)

A post-study medical will be performed 12 weeks following the first study vaccine administration and the following assessments will be carried out: an assessment of the injection site, a pharmacodynamic blood sample will be taken to measure antibody response, physical examination, vital signs, 12-lead ECG, urinalysis, blood samples for haematology and biochemistry, serum pregnancy test (if applicable) and a review of AEs and concomitant medications.

Safety Follow-Up (Visit 11)

A safety follow-up phone call will be performed 3 months after the end of the study (Visit 10) i.e. 6 months following the first study vaccine administration to check the general health of the volunteer and to review significant AEs.

[REDACTED]

In both Part A and Part B, following the primary dose volunteers will remain in the study unit for 8 hours post-dose to ensure that no significant AEs occur and the medicinal product is well tolerated. No additional acute safety concerns are considered likely to occur following 8 hours of observation. Following the booster dose volunteers will remain

in the clinic for at least 4 hours post-dose, as the volunteer has tolerated the initial dose, and therefore, tolerability should be consistent. The concern is for an acute systemic reaction following the booster dose. It is not considered necessary to keep the volunteers in the study unit overnight as no samples are being taken and the time intervals are considered appropriate to assess the safety and tolerability prior to discharge.

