12.6 Individual Volunteer Stopping Criteria

Volunteers who meet one or more of the following stopping criteria will receive no further doses of study vaccine but will be followed up for safety:

- Severe injection site reaction, see Appendix 1
- Severe systemic reaction, e.g. anaphylaxis, see section 14.2.1
- Persistent febrile reaction (>38.9°C and >24 hours) at the Investigator's discretion
- SAE related to the study agent

The medical safety of the volunteer is of paramount importance when discussing study continuation.

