14.3 Recording and Follow up of Adverse Events

Up to Day 85 (Visit 10), the volunteers will be instructed to spontaneously report all AEs to the site staff or Investigator as soon as possible. Any AEs observed or reported by a volunteer and/or staff up to Day 85 (Visit 10) will also be recorded in the eCRF. The Investigator will review results from the physical examinations. All new and aggravated findings, as compared with baseline, must be identified and recorded as AEs in the eCRF. In Part B, following Day 85 (Visit 10) AEs will be recorded by the volunteer in a diary card, and only relevant or significant AEs will be recorded in the eCRF.

AEs already recorded and designated as 'continuing' should be reviewed at each subsequent assessment.

For all AEs, the Investigator must obtain adequate information to determine the outcome of the AE and to assess whether it meets the criteria for classification as an SAE. For all AEs, sufficient information should be obtained by the Investigator to determine the causality of the AE (i.e. study vaccine or other illness). The Investigator is required to assess causality and record that assessment on the eCRF. Follow-up of the AE, after the date of therapy discontinuation, is required if the AE or its sequelae persist. Any AE that is still ongoing at the post-study medical visit will have an outcome of 'ongoing' recorded in the eCRF,

however the Investigator will continue to follow up ongoing related AEs and record information in the source documents. Related SAEs will be followed until the event resolves or the event or sequelae stabilise and this information will be reported to the Sponsor using the SAE reporting forms.

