18. SCHEDULE OF ASSESSMENTS

Part A Schedule of Assessments

	Screening Period	Treatment Period								Post-Study Medical	Safety Follow-Up
	Visit 1	Visit 2	Visit 3	Visit 4	Visit 5	Visit 6	Visit 7	Visit 8	Visit 9	Visit 10	Visit 11
Assessment	Day -28 to Day -1	Day 1	Day 2	Day 8	Day 15 ^a	Day 29 ^b	Day 30 ^{b,c}	Day 43 ^b	Day 57 ^b	Day 85	Day 183 ^a
Informed Consent	X										
Inclusion/ Exclusion Criteria	X										
Demography	X										
Medical History	X										
Physical Examination ^d	X	X								X	
Height, Weight, BMI	X										
Vital signs ^e	X	X ^f	X	X		X ^{g,h}	X	X		X	
12-lead ECG	X									X	
Urinalysis	X			X				X		X	
Safety laboratory tests	X			X				X		X	
HIV, Hep B and Hep C	X										
Pregnancy test ⁱ	X	X				X ^h				X	
Alcohol breath test	X	X									
Urine drugs of abuse test	X	X									
Review of volunteer eligibility		X									
Randomisation		X									
Administration of primary dose ^l		X									
Administration of booster dose						X ^h					
PD blood sample – antibody response		X				X		X	X	X	
Brief medical examination ^k		X				X					
Assessment of injection site(s) ^l			X	X		X ^m	X	X	X	X	
AE check						X				X	X
Con med check	X					X				X	

Footnotes

- a. Visit performed by telephone.
- b. Day numbers of Visits 6, 7, 8 and 9 may change if the dosing regimen is changed.
- c. Visit 7 not required if booster dose not administered.
- d. Full physical examination at screening and post-study medical. Brief physical examination prior to first dose.
- e. Heart rate, blood pressure, tympanic temperature and respiration rate.
- f. Vital signs at Visit 2 will be recorded pre-dose and at 2 and 6 hours post-dose.
- g. Vital signs at Visit 6 will be recorded pre-dose and at 2 hours post-dose.
- h. Administration of booster dose only if applicable to this cohort. If booster dose not administered, vital signs and pregnancy test are not to be performed.
- i. Serum pregnancy test at screening and post-study medical. Urine pregnancy test prior to each dose.
- j. Sentinel dosing for all cohorts for the primary dose only.
- k. Brief medical examination (including assessment of the injection site(s) to determine eligibility for discharge at least 8 hours post-dose on Day 1 and at least 4 hours post-dose on Day 29.
- l. Photographs may be taken of injection site reactions as required.
- m. Assessment of first injection site, to be assessed pre-dose.

Part A Schedule of Assessments – Exploratory Assessments

	Treatment Period				Post-Study Medical

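### Part A: Section 12.5 removes a volunteer who meets a stopping criterion from the study, while Section 12.6 stops only her dosing and keeps her in safety follow-up

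*Combined protocol and SAP*

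**What the plan says.** Section 12.5, headed as applying to Part A only, deals with the Safety Monitoring Board and dose escalation. Near its end it states: "Individual volunteers will be discontinued from the study if they meet any of the individual volunteer stopping criteria as described in Section 12.6".

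Section 12.6 lists the criteria: a severe injection-site reaction, a severe systemic reaction, a persistent febrile reaction (at the Investigator's discretion) and a related SAE. Volunteers who meet one "will receive no further doses of study vaccine but will be followed up for safety". It names no visits.

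Three other places bear on the outcome:

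- Section 9.5 covers participation that ends early: "A post-study medical should be performed as described in Section 12.2". For Part A, Section 12.2.1 times that examination as follows: "A post-study medical will be performed 12 weeks following the first study vaccine administration".
- Section 14.3 on adverse events: "Any AEs observed or reported by a volunteer and/or staff up to Day 85 (Visit 10) will also be recorded in the eCRF". It also requires follow-up of events that persist after vaccination stops.
- Section 15.4.2 keeps withdrawn volunteers and dropouts in the safety analysis (ITT).

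**The concern.** Leaving the study and stopping vaccination are different events. The first ends scheduled visits; the second does not. The protocol attaches both to the same trigger, in adjacent sections of current text, and no clause says which prevails.

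The volunteers concerned have had a severe reaction, a persistent fever or a related SAE in the first human study of this vaccine. The primary objective is safety and tolerability for 12 weeks after the first dose, so they are the people whose later laboratory values, vital signs and injection sites matter most. Keeping them in the ITT set does not recover measurements that were never taken, and Section 15.2 says that missing data are in general not replaced.

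For a volunteer who reacts after the booster, dosing is already complete. The only thing Section 12.5 can then do is end her follow-up.

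The missing visit list in Section 12.6 is a lesser matter of detail. It has one practical consequence: Section 15.1.1 restricts post-vaccination summaries to scheduled assessments, so values from ad hoc follow-up might not enter them.

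**Working it through.** The plan gives no figure to reproduce. The check compares the two texts and then counts what the literal reading of Section 12.5 would remove.

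**Texts side by side.** The trigger is the same, any Section 12.6 criterion. The consequence in Section 12.5 is the end of study participation. The consequence in Section 12.6 is the end of dosing with safety follow-up. Section 9.5 supplies the pathway only when participation ceases. The no-booster notes in the Part A schedule (for example "Visit 7 not required if booster dose not administered") say what is omitted without a booster, but are not tied to the stopping criteria. None of these settles which route a stopped volunteer takes.

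**Inputs for the count.** The Part A Schedule of Assessments (Section 18) and the visit descriptions in Section 12.2.1. The comparator is full attendance at the remaining visits. That is an assumption, because Section 12.6 lists none. A volunteer stopped before the booster has no Visit 7 and no Visit 6 vital signs.

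**Formula.** Lost = remaining scheduled assessments − 1, because one post-study medical supplies one of each kind.

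| Assessment | Remaining if stopped at Day 2 | Lost | Remaining if stopped at Day 30 | Lost |
|---|---|---|---|---|
| Laboratory tests and urinalysis | Days 8, 43, 85 = 3 | 3 − 1 = 2 | Days 43, 85 = 2 | 2 − 1 = 1 |
| Vital signs | Days 8, 43, 85 = 3 | 3 − 1 = 2 | Days 43, 85 = 2 | 2 − 1 = 1 |
| Injection-site check | Days 8, 29, 43, 57, 85 = 5 | 5 − 1 = 4 | Days 43, 57, 85 = 3 | 3 − 1 = 2 |
| Adverse event review | Days 8, 15, 29, 43, 57, 85, 183 = 7 | 7 − 1 = 6 | Days 43, 57, 85, 183 = 4 | 4 − 1 = 3 |

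The counts do not depend on when the medical is done. If it is held at Day 85 for the Day 2 case, the losses are Days 8 and 43 (2), Days 8 and 43 (2), Days 8, 29, 43 and 57 (4), and Days 8, 15, 29, 43, 57 and 183 (6).

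**Timing of the medical.** Section 9.5 refers to Section 12.2, which sets Week 12. It does not say whether the examination is brought forward after an early withdrawal. The interval from the medical to Day 85 is therefore between 85 − 85 = 0 and 85 − 2 = 83 days for a stop at Day 2, and between 0 and 85 − 30 = 55 days for a stop at Day 30.

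**Lower bound.** If the site follows Section 12.6 and keeps the volunteer on the schedule, every loss in the table is 0.

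**The case against.** The best defence is that Section 12.5 contains only a one-line pointer, within a passage about escalation, and sends the reader to Section 12.6, where the operative rule is correct. On this view the wording is loose and a careful investigator would apply Section 12.6. The post-booster case supports this, since nobody would intend a rule whose only effect is to end follow-up. Most of this stands. Section 12.6 is probably the intent, and this lowers the severity. It does not remove the contradiction: grammatically the cross-reference covers the criteria, not the consequence, and the sentence still says that the volunteer leaves the study.

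A second defence is that the Schedule of Assessments is the natural default for anyone still in follow-up, so Section 12.6 needs no list. That is reasonable, and it is why the missing list counts as missing detail. It applies equally to Part B, where the contradiction itself does not arise.

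A reader might infer that Section 12.3 settles the matter, since it says that "the total number of safety assessments per volunteer will not be reduced". It does not. That clause concerns assessment times that move as the study yields information, not volunteers who have been stopped. It neither guarantees the visits nor shows intent with any force.

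A reader might also infer that stopped volunteers disappear from safety evaluation. The documents do not support this. Section 14.3 keeps recording events reported or observed up to Day 85 and follows those that persist, Section 14.5.1 keeps SAE reporting, Section 9.5 requires a post-study medical, and Section 15.4.2 keeps the volunteer and her triggering event in the analysis. What is at risk is scheduled measurement and active questioning.

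**Conclusion.** The point holds: Section 12.5 is wrong as written for Part A, at low to moderate severity. Read literally, it costs a volunteer stopped at Day 2 without a booster 2 of 3 laboratory and urinalysis sets, 2 of 3 vital-sign sets, 4 of 5 injection-site checks and 6 of 7 adverse event reviews. For a stop at Day 30 after the booster the figures are 1 of 2, 1 of 2, 2 of 3 and 3 of 4. All but the Day 183 call fall within the primary safety period.

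These sizes rest on two assumptions: that Section 12.5 is applied literally, and that full attendance is the right comparator. If less follow-up was intended the loss is smaller, and under Section 12.6 with the full schedule it is zero. The documents do not say how many volunteers would be affected. A reader might try to take a number from the Section 12.7 percentage rule, but that rule only triggers a review meeting and does not estimate how many volunteers are stopped.

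**What to change.** In Section 12.5, replace the words that remove the volunteer from the study with: *discontinued from further study vaccination and followed up for safety as described in Section 12.6*.

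In Section 12.6, add: *Unless consent is withdrawn or the volunteer is withdrawn under Section 9.5, follow-up means the remaining scheduled safety assessments for her study part (Part A: through Visit 10 and the Visit 11 call; Part B: through Visit 20), omitting assessments that apply only when a booster is given.*

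The exception for Section 9.5 is needed because that section makes the Sponsor and the Investigator responsible for withdrawing a volunteer when this is in her best interest. An exception for withdrawn consent alone would override it.

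The cost is one sentence in each section. There are no new visits and no change to sample size, analysis sets or escalation rules. The documents do not say whether Part A is still dosing. If it has finished, the Section 12.5 edit has little practical effect, but the Section 12.6 sentence remains useful for Part B.
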